9.7. Pregnancy

Pregnancy, in and of itself, is not regarded as an AE unless there is suspicion that the study treatment may have interfered with the effectiveness of a contraceptive medication or method. When a pregnancy has been confirmed in a participant during maternal or paternal exposure to study treatment, the following procedures should be followed in order to ensure safety:

- The study treatment must be discontinued immediately (female participants only).
- The investigator must complete and submit the Incyte Clinical Trial Pregnancy Form to the sponsor or its designee within **24 hours** of learning of the pregnancy.

Data on fetal outcome are collected for regulatory reporting and drug safety evaluation. Follow-up should be conducted for each pregnancy to determine outcome, including spontaneous or voluntary termination, details of the birth, and the presence or absence of any birth defects, congenital abnormalities, or maternal and/or newborn complications, by following until the first well-baby visit. Pregnancy should be recorded on a Clinical Trial Pregnancy Form and reported by the investigator to the sponsor or its designee. Pregnancy follow-up information should be recorded on the same form and should include an assessment of the possible causal relationship to the sponsor's study drug to any pregnancy outcome, as well as follow-up to the first well-baby visit or the duration specified in local regulations, whichever is later. Refer to the Incyte Reference Guide for Completing the Clinical Trial Pregnancy Form in the Study Binder.

Any SAE occurring during pregnancy of a study participant must be recorded on the Serious Adverse Event Report Form and submitted to the sponsor or its designee.

Abnormal pregnancy outcomes (eg, spontaneous abortion, fetal death, stillbirth, congenital anomalies, or ectopic pregnancy) are considered SAEs (if occurring in the study participant) and

must be reported as described in Section 9.4. If an abnormal pregnancy outcome is reported in a study participant's partner, the event should be reported to the sponsor on the Clinical Trial Pregnancy Form.

9.8. Warnings and Precautions

Special warnings or precautions for the study treatment, derived from safety information collected by the sponsor or its designee, are presented in the [parsaclisib IB](#) and [ruxolitinib IB](#). Additional safety information collected between IB updates will be communicated in the form of Investigator Notifications. Any important new safety information should be discussed with the participant during the study as necessary. If new significant risks are identified, they will be added to the ICF.

9.9. Product Complaints

The sponsor collects product complaints on study drugs and drug delivery systems used in clinical studies in order to ensure the safety of study participants, monitor quality, and facilitate process and product improvements.

All product complaints associated with material packaged, labeled, and released by the sponsor or its designee will be reported to the sponsor. All product complaints associated with other study material will be reported directly to the respective manufacturer.

The investigator or his/her designee is responsible for reporting a complete description of the product complaint via e-mail or other written communication to the sponsor contact or respective manufacturer as noted in the packaging information. Any AE associated with a product complaint should be recorded as described in Section 9.3.

If the investigator is asked to return the product for investigation, he/she will return a copy of the product complaint communication with the product.

9.10. Treatment of Overdose

There has been no clinical experience with overdose of parsaclisib. Treatment of overdose should consist of general supportive measures.

Refer to the approved product label of ruxolitinib for advice on overdose.

10. STATISTICS

10.1. Sample Size Determination

The primary endpoint of this study is the proportion of participants with $\geq 35\%$ spleen volume reduction from baseline to Week 24 as measured by MRI (or CT scan in applicable participants). The primary endpoint will be analyzed by CMH test stratified by DIPSS (intermediate-1 vs intermediate-2 vs high) and baseline (or screening, if applicable) platelet count ($\geq 100 \times 10^9/L$ vs 50 to $< 100 \times 10^9/L$ inclusive; note that if a participant's platelet count is $< 50 \times 10^9/L$ at baseline, the platelet count at screening will be used for stratification/randomization). Assuming a 58.2% (29.4%) response rate for participants with normal (low) platelet count for the ruxolitinib plus piasalisib group versus 41.0% (17.2%) response rate for participants with normal (low) platelet count for the ruxolitinib plus placebo group, to achieve 83.67% power to detect a statistically significant difference with a 2-sided Type I error of 5%, a sample size of 440 participants is required to be randomized equally between treatment groups.

For the key secondary endpoint of proportion of participants who have a $\geq 50\%$ in MFSAF TSS from baseline to Week 24, assuming a response rate of 61.7% (50.0%) for participants with normal (low) platelet count for the ruxolitinib plus piasalisib group and a response rate of 45.9% (34.5%) for participants with normal (low) platelet count for the ruxolitinib plus placebo group, a sample size of 440 will provide 80.02% power using CMH test given a 2-sided Type I error of 5%.

A test for OS will be performed when 85 deaths are observed using the log-rank test stratified by platelet count and DIPSS at baseline at a 2-sided Type I error level of 0.05. The log-rank test will provide 80% power to detect a hazard ratio of 0.54. Assuming a median survival time of 5.3 years for ruxolitinib plus placebo and enrollment duration is 1.5 years, the expected time to analysis from the first participant randomized is 3 years.

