1. PROTOCOL SUMMARY

Protocol Title: A Phase 3, Randomized, Double-Blind, Placebo-Controlled Study of the Combination of PI3K δ Inhibitor Parsaclisib and Ruxolitinib in Participants With Myelofibrosis

Protocol Number: INCB 50465-313

Objectives and Endpoints:

Table 1 presents the primary and major/key secondary objectives and endpoints.

Table 1: Primary and Secondary Objectives and Endpoints

Objectives	Endpoints
Primary	
To evaluate and compare the efficacy of parsaclisib plus ruxolitinib versus placebo plus ruxolitinib on spleen volume at Week 24.	Proportion of participants achieving $\geq 35\%$ reduction in spleen volume from baseline to Week 24 as measured by MRI (or CT scan in applicable participants).
Major/Key Secondary	
To evaluate and compare the effect of parsaclisib plus ruxolitinib versus placebo plus ruxolitinib on participant reports of MF symptoms.	Proportion of participants who have a $\geq 50\%$ reduction in TSS from baseline to Week 24 as measured by the MFSAF v4.0 diary. Change in TSS from baseline to Week 24 as measured by the MFSAF v4.0 diary. Time to the first $\geq 50\%$ reduction in TSS as measured by the MFSAF v4.0 diary.
To evaluate and compare the effect of parsaclisib plus ruxolitinib versus placebo plus ruxolitinib with respect to OS.	OS determined from the date of randomization until death due to any cause.
To evaluate and compare the safety and tolerability of parsaclisib plus ruxolitinib versus placebo plus ruxolitinib.	Safety and tolerability will be assessed by monitoring the frequency and severity of AEs, performing physical examinations, and evaluating changes in vital signs, ECGs, and laboratory results.

Overall Design:

Table 2 presents the key study design elements. Further study details are presented after the table.

Table 2: Key Study Design Elements

Study Phase	Phase 3
Clinical Indication	Treatment of patients with primary and secondary MF
Population	Participants with primary or secondary MF with DIPSS risk category of intermediate or high who are in need of treatment for MF and are naive to both prior JAK inhibitor and prior PI3K inhibitor therapy
Number of Participants	Approximately 440 participants will be randomized 1:1 to 1 of 2 groups. Note: Certain countries must meet a minimum enrollment regulatory requirement; therefore, enrollment in these countries may continue after enrollment in other countries ends. Group A: pascalisib plus ruxolitinib Group B: placebo plus ruxolitinib

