4.1.2. Unblinding and Crossover

When the last enrolled participant has completed the Week 24 assessments and the data entered by all sites for all participants has been verified and cleaned through the Week 24 visit (including imaging), the database will be frozen. The study will then be unblinded, and participants randomized to placebo will have the opportunity to cross over to begin receiving parsaclisib, together with continued ruxolitinib, as long as hematology parameters are adequate (see Section 6.4 for hematology requirements). Similarly, participants found to have been randomized to parsaclisib will continue treatment with parsaclisib, together with continued ruxolitinib, as long as the regimen is tolerated and the participant does not meet discontinuation criteria.

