6.4. Dose and Requirement to Start Dosing After Crossover

After criteria for crossover have been met (early or for entire study) and sites have received notification that unblinding and crossover may occur, the crossover visit will be scheduled and dosing with parsaclisib will begin as long as the following hematology criteria are met based on a laboratory visit within 2 weeks of the planned parsaclisib start date:

- The platelet count is at least $50 \times 10^9/L$.
- The ANC is at least $0.5 \times 10^9/L$.

No more than 3 repeat assessments for platelet count and ANC are allowed. Participants who have received 1 or more platelet transfusions must have a platelet count $\geq 50 \times 10^9/L$ at least 7 days after the most recent platelet transfusion to qualify for crossover. Participants in whom the platelet count and/or ANC remain below these thresholds at the time of the later of (a) 4 weeks or (b) the next regularly scheduled study visit following the date at which it was

determined that crossover could occur will be discontinued from the study and that visit will constitute the EOT.

The dose of piasalisib will be 5 mg QD, taken in the morning, without regard to food.

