7.1.2. Discontinuation Procedures

The decision to discontinue study treatment and reference treatment will not constitute study withdrawal or study completion. In the event that the decision is made to discontinue study treatment and reference treatment, the treatment portion will be considered complete and the follow-up part of the study will begin.

If a participant is discontinued from study treatment:

- The study monitor or sponsor must be notified.
- The reason(s) for discontinuation must be documented in the participant's medical record and the primary reason for discontinuation must be included in the eCRF.
- The EOT visit should be performed and date recorded.
- The last date of the last dose of study drug/reference treatment will be recorded in the eCRF.
- The status of the participant should be updated to EOT in the IXRS.

- Participants must be followed for safety until the time of the follow-up visit or until study drug/reference treatment–related toxicities resolve, return to baseline, or are deemed irreversible, whichever is longest.
- Participants will be followed for subsequent MF treatment regimens and survival via periodic telephone contact. Results of these contacts will be recorded in the eCRF.

If the participant discontinues study treatment/reference treatment and actively withdraws consent for collection of follow-up data (safety follow-up or disease assessment), then no additional data collection should occur; however, participants will have the option of withdrawing consent for study treatment/reference treatment and further assessments but allowing survival follow-up.

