10.2. Populations for Analysis

The populations for analysis are provided in [Table 16](#).

Table 16: Populations for Analysis

Population	Description
ITT	All randomized participants. The ITT population will be used for the summary of demographics, baseline characteristics, participant disposition, and analyses of all efficacy data. Participants will be analyzed according to the treatment group to which they were randomized regardless of the treatment received during the study.
Safety	All randomized participants who received at least 1 dose of piasalisib, placebo, or ruxolitinib. Treatment groups for this population will be determined according to the actual treatment the participant received regardless of assigned study drug treatment. All safety analyses will be conducted using the safety population.
PP	Participants in the ITT population who are considered to be sufficiently compliant with the Protocol.

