10.3. Level of Significance

This study defines a single primary endpoint with a single primary analysis. The study will be claimed to have achieved the primary efficacy objective when the primary endpoint shows a significant result at a 2-sided alpha level of 0.05 at final analysis. The secondary efficacy endpoints will be analyzed only when the study has reached the efficacy objective in the primary endpoint. The key secondary efficacy variables will be tested following a fixed-sequence-testing procedure with each at the 2-sided alpha level of 0.05 in the order below:

1. The proportion of participants who have a $\geq 50\%$ reduction from baseline to Week 24 in the MFSAF TSS.
2. OS.

Other secondary [REDACTED] endpoints will be tested using a 2-sided, 5% significance level but are not considered alpha-controlled hypotheses.

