5. STATISTICAL METHODOLOGY

5.1. General Methodology

Unless otherwise noted, SAS® software (SAS Institute Inc, Cary, NC; v9 or later) will be used for the generation of all tables, graphs, and statistical analyses. Descriptive summaries for continuous variables will include but not be limited to the number of observations, mean, standard deviation, median, minimum, and maximum. Descriptive summaries for categorical variables will include the number and percentage of participants in each category.

A participant randomized to the placebo group may cross over to parsaclisib treatment if the participant meets the criteria for an early crossover defined in Protocol Section 4.1.3. Unless specified, efficacy and safety analyses for between-treatment comparisons (parsaclisib vs placebo) will be conducted using the data truncated at the time of treatment crossover for those participants who make an early treatment crossover.

Interim analyses are planned for this study as defined in Section 10.

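### Is the 80% overall-survival power overstated because placebo participants may cross over to parsaclisib before the test?

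*Protocol*

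**What the plan says.** Protocol 10.1 and SAP 3.3 make the same OS statement: a stratified log-rank test at 85 deaths, two-sided 5%. "The log-rank test will provide 80% power to detect a hazard ratio of 0.54". For timing they assume a control median of 5.3 years and 1.5 years of enrollment, and expect the analysis 3 years after the first randomization. Crossover is not mentioned, and 0.54 is not labelled as an effect with or without switching.

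Protocol 4.1.2 opens crossover to the whole control arm after the last participant's Week 24 data have been cleaned and frozen. Those "randomized to placebo will have the opportunity to cross over to begin receiving parsaclisib, together with continued ruxolitinib, as long as hematology parameters are adequate". Several provisions limit or delay this:

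- Protocol 6.4: "dosing with parsaclisib will begin as long as the following hematology criteria are met".
- Protocol 7.1.2, for a participant who has stopped treatment: "the treatment portion will be considered complete and the follow-up part of the study will begin".
- Protocol 1, Table 2, for countries with an enrollment minimum: "enrollment in these countries may continue after enrollment in other countries ends".

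The primary OS analysis (Protocol Table 17) is the stratified log-rank in the ITT population, for which Protocol 10.2 says: "Participants will be analyzed according to the treatment group to which they were randomized regardless of the treatment received during the study". SAP 7.4.3 censors only participants who are alive or lost to follow-up, and plans a rank-preserving structural failure time analysis as a sensitivity analysis. SAP 5.1 truncates data for a placebo participant who "meets the criteria for an early crossover defined in Protocol Section 4.1.3"; SAP 5.2 limits this to crossover before Week 24. Neither covers the study-wide crossover. On multiplicity, Protocol 10.3 says: "The key secondary efficacy variables will be tested following a fixed-sequence-testing procedure". OS is second in that sequence.

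**The concern.** The power figure comes from one constant hazard ratio, yet the design lets control participants start the test drug before the OS analysis. If parsaclisib prolongs survival, switching pulls the arms together and the ITT test sees a hazard ratio nearer 1. The truncation rules do not reach the study-wide crossover, and the rank-preserving analysis is supportive, so neither protects the power of the alpha-controlled test. At stake is how a non-significant OS result would be read: as a miss that had a planned chance of 20%, or as one that was materially more likely.

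**Working it through.** **1. The plan's own figure.** Inputs from Protocol 10.1: hazard ratio 0.54, two-sided 5%, 1:1 allocation, 85 deaths. By Schoenfeld's formula, the deaths needed for 80% power are

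4 × (1.960 + 0.842)² / (ln 0.54)² = 4 × 7.849 / 0.3797 = 82.7.

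At 85 deaths, z = (√85 / 2) × 0.6162 − 1.960 = 2.841 − 1.960 = 0.881, which is 81.1% power. Freedman's formula gives 78.6%. The stated 80% is sound for a hazard ratio of 0.54 as seen by the test.

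**2. When crossover can open.** 1.5 + 24 × 7 / 365.25 = 1.96 years. This is a floor: cleaning, freeze, unblinding, the crossover visit and any extended enrollment all come on top.

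**3. Deaths left to be affected.** Model: exponential survival, control median 5.3 years, uniform 1.5-year accrual, 220 per arm, hazard ratio 0.54, no loss to follow-up, no crossover. The 85th death falls at 2.91 years.

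| Opening (years) | Expected deaths before opening (placebo + parsaclisib) | Remaining of 85 |
|---|---|---|
| 1.96 | 31.9 + 17.9 = 49.8 | 35.2 |
| 2.1 | 35.3 + 19.9 = 55.2 | 29.8 |
| 2.4 | 42.4 + 24.1 = 66.5 | 18.5 |
| 2.7 | 49.2 + 28.2 = 77.5 (rounded) | 7.5 |

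**4. Does the stated 3 years reveal the intended reading?** No. The 85th death falls at 2.91 years without crossover and between 2.91 and 3.19 years across the crossover scenarios.

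**5. Reading A: 0.54 is the ITT hazard ratio.** Step 1 applies as it stands. This is the ordinary reading, because Protocol 10.1 gives the hazard ratio to be detected by a log-rank test that Protocol 10.2 and Table 17 define by randomized arm.

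**6. Reading B: 0.54 is the effect without switching.** Opening time, uptake, post-switch effect and treatment discontinuation must all be assumed. The table gives simulated power (6,000 trials per setting, Monte Carlo standard error about 0.5 to 0.65 points, unstratified log-rank at the 85th death, early crossover left out). Uptake is 30/50/80% of placebo participants alive and still on treatment, with 20% yearly discontinuation; figures for 40% are in parentheses. Half benefit means half the log hazard ratio.

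| Opening (years) | Full benefit after switch | Half benefit |
|---|---|---|
| 2.1 | 75/70/62% (76/74/69%) | 77/75/72% (78/77/74%) |
| 2.4 | 78/75/70% (77/78/75%) | 79/78/75% (79/79/76%) |
| 2.7 | 79/78/77% (80/79/78%) | 80/78/78% (80/79/78%) |

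With no crossover the simulation gives 80.7%. With switching but no post-switch benefit it gives 79 to 81% at every opening time and uptake. The lowest value found, 49%, needs opening at exactly 1.96 years and 80% uptake among all placebo survivors, including those already off treatment. The cleaning step in Protocol 4.1.2 and the discontinuation rule in Protocol 7.1.2 make that a bound, not a plausible case.

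**7. Reading B is itself incomplete.** The table applies discontinuation only to placebo participants' eligibility to switch; parsaclisib participants keep 0.54 after stopping drug. If the benefit instead ended with treatment (also an assumption), power with no crossover at all would be about 57% at 20% yearly discontinuation and 37% at 40% (4,000 trials each). An on-drug 0.54 therefore has no definite power until several more inputs are chosen. The ITT hazard ratio is the quantity for which the plan's statement is complete.

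**The case for a change.** The best case for a change is that something goes unsaid on either reading. If 0.54 excludes switching, 80% is optimistic. If it includes switching, the design relies on a stronger underlying effect that is not given: with opening at 2.1 to 2.4 years and 50 to 80% uptake among those on treatment, about 0.46 to 0.53 (full benefit) or 0.50 to 0.53 (half). Those ranges carry the same simplification as step 7. The SAP's own rank-preserving analysis shows that the sponsor expected crossover to affect OS, and a clarifying sentence would cost little.

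The missing label is real, and so is the possible optimism of 0.54 as an ITT effect. But a target hazard ratio in a power statement is an assumption, and nothing in the documents shows that this one was meant to exclude switching. A label would alter no decision in the trial: the event count, alpha, test, population and data collected would be the same. If parsaclisib has no effect on survival, switching changes nothing, so Type I error is not inflated; if it helps, the ITT estimate moves toward 1, which is conservative. A reader of a non-significant OS result will have the estimate, its confidence interval and the crossover-adjusted sensitivity analysis, which tell more than the planned power does.

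**Conclusion.** No change is called for. The 80% is correct for a hazard ratio of 0.54 between randomized arms (81.1% by Schoenfeld at 85 deaths), and that is what an ITT log-rank test detects. A loss appears only under a different meaning of 0.54, combined with a survival benefit from switching and with uptake, timing and discontinuation that the documents do not give. With opening at 2.1 to 2.4 years, 30 to 80% uptake and 20% yearly discontinuation, that reading gives about 62 to 78% (full benefit) or 72 to 79% (half). With later opening, or no post-switch benefit, it is at or close to 80%. Offering crossover at some cost to the last endpoint in the sequence is a fair trade-off, and the plan accompanies it with an adjusted analysis. What remains is a missing label that a statistician would fill sensibly by reading 0.54 as the ITT hazard ratio. No stated power is shown to be undelivered.

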10.2. Populations for Analysis

The populations for analysis are provided in [Table 16](#).

Table 16: Populations for Analysis

Population	Description
ITT	All randomized participants. The ITT population will be used for the summary of demographics, baseline characteristics, participant disposition, and analyses of all efficacy data. Participants will be analyzed according to the treatment group to which they were randomized regardless of the treatment received during the study.
Safety	All randomized participants who received at least 1 dose of piasalisib, placebo, or ruxolitinib. Treatment groups for this population will be determined according to the actual treatment the participant received regardless of assigned study drug treatment. All safety analyses will be conducted using the safety population.
PP	Participants in the ITT population who are considered to be sufficiently compliant with the Protocol.

